4.3.1 Justification for Non-investigational Product Dose

Not applicable

4.4 End of Study

4.4.1 End of Study Definition

Primary Completion: The primary completion date is defined as the date when the last subject is assessed or receives an intervention for the final collection of data for the primary endpoint(s).

If the study concludes prior to the primary completion date originally planned in the protocol (ie, early termination of the study), then the primary completion will be the date when the last subject is assessed or receives an intervention for evaluation in the study (ie, last subject last visit).

End of Study: The end of study date is defined as the date when the last subject across all sites is assessed or receives an intervention for evaluation in the study (ie, last

subject last visit), following any additional parts in the study (eg, long-term follow-up, additional antibody testing), as applicable.

4.4.2 Study Duration for Subjects

The expected study duration for subjects will be approximately 121 days, including up to 14 days for screening activities, 77 (cohort 1) or 56 (cohort 2) days for treatment with AMG 330 in combination with pembrolizumab, and 30 days for safety follow-up.

Subjects in both cohort 1 and cohort 2 may continue to repeat cycles of AMG 330 and pembrolizumab up to 6 months if the dose of the combination regimen remains tolerable and the subject is deriving benefit in the opinion of the investigator. The duration of the combination treatment period for individual subjects may be extended up to 1 year if the subject is deriving benefit in the opinion of the investigator and after consultation with sponsor. If AMG 330 is discontinued, pembrolizumab may be continued as a monotherapy until disease progression for a maximum of 35 cycles (approximately 2 years). If either study drug is discontinued, the other may be continued as a monotherapy.

4.5 Patient Input on Study Design

Not applicable

5. Study Population

Investigators will be expected to maintain a screening log of all potential study candidates that includes limited information about the potential candidate (eg, date of screening).

Eligibility criteria will be evaluated during screening.

Before any study-specific activities/procedures, the appropriate written informed consent must be obtained (see [Section 11.3](#)).

Prospective approval of protocol deviations to recruitment and enrollment criteria, also known as protocol waivers or exemptions will not be provided.

5.1 Inclusion Criteria

Subjects are eligible to be included in the study only if all of the following criteria apply:

- 101 Subject has provided informed consent prior to initiation of any study specific activities/procedures.
- 102 Age \geq 18 years on day of signing informed consent.
- 103 AML as defined by the WHO Classification ([Section 11.10](#)) persisting or recurring following 1 or more treatment courses. Exception: promyelocytic leukemia (APML) is excluded from the study.

104 More than 5% blasts in bone marrow.

105 Eastern Cooperative Oncology Group (ECOG, [Section 11.9](#)) Performance Status of ≤ 1 .

106 Have adequate organ function as defined in [Table 5-1](#). Specimens must be collected within 14 days prior to study day 1.

Table 5-1. Adequate Organ Function Laboratory Values

System	Laboratory Value
Renal	
Measured or calculated ^a creatinine clearance (GFR can also be used in place of creatinine or CrCl)	≥ 30 mL/min for participant with creatinine levels $> 1.5 \times$ institutional ULN
Hepatic	
Total bilirubin	$\leq 1.5 \times$ ULN OR direct bilirubin \leq ULN for participants with total bilirubin levels $> 1.5 \times$ ULN
AST (SGOT) and ALT (SGPT)	$\leq 2.5 \times$ ULN
Coagulation	
International normalized ratio (INR) OR prothrombin time (PT) Activated partial thromboplastin time (aPTT)	$\leq 1.5 \times$ ULN unless participant is receiving anticoagulant therapy as long as PT or aPTT is within therapeutic range of intended use of anticoagulants
ALT (SGPT) = alanine aminotransferase (serum glutamic pyruvic transaminase); AST (SGOT) = aspartate aminotransferase (serum glutamic oxaloacetic transaminase); GFR = glomerular filtration rate; ULN = upper limit of normal. ^a Creatinine clearance (CrCl) should be calculated per institutional standard. Note: This table includes eligibility-defining laboratory value requirements for treatment; laboratory value requirements should be adapted according to local regulations and guidelines for the administration of specific chemotherapies.	

107 A male participant must agree to use contraception during the treatment period and for at least 120 days after receiving the last dose of study drug (AMG 330 or pembrolizumab).

- Acceptable methods of highly effective birth control include sexual abstinence; vasectomy; or a condom with spermicide (men) in combination with hormonal birth control or intrauterine device (IUD) (women).
- Males will not be allowed to donate sperm during this period.

108 A female participant is eligible to participate if she is not pregnant, not breastfeeding, and at least 1 of the following conditions applies:

- Not a woman of childbearing potential (WOCBP)
- A WOCBP who agrees to follow contraceptive guidance during the treatment period and for at least 120 days after the last dose of study treatment (AMG 330 or pembrolizumab)
- Acceptable methods of highly effective birth control include sexual abstinence; bilateral tubal ligation/occlusion; or a condom with spermicide (men) in combination with hormonal birth control or IUD (women).

5.2 Exclusion Criteria

Subjects are excluded from the study if any of the following criteria apply:

Disease Related

201 Active extramedullary AML in the central nervous system (CNS).

Other Medical Conditions

202 Prior malignancy (other than in situ cancer) unless treated with curative intent and without evidence of disease for > 2 years before screening.

Note: Participants with basal cell carcinoma of the skin, squamous cell carcinoma of the skin, or carcinoma in situ (eg, breast carcinoma, cervical cancer in situ) that have undergone potentially curative therapy are not excluded.

203 History or evidence of significant cardiovascular risk including any of the following: symptomatic congestive heart failure, unstable angina, clinically significant arrhythmias (eg, ventricular fibrillation, ventricular tachycardia etc.), recent coronary angioplasty, intra-cardiac defibrillators or any clinically relevant concurrent disorder that may pose a risk to subject safety or interfere with study evaluation, procedures, or completion.

204 History of arterial thrombosis (eg, stroke or transient ischemic attack) in the past 12 months.

205 Active infection requiring IV antibiotics within 1 week of study enrollment (day 1).

206 Known positive test for human immunodeficiency virus (HIV).

207 History of chronic or active hepatitis B (known to be positive for hepatitis B surface antigen [HBsAg] or quantifiable hepatitis B virus [HBV] viral load). Positive for hepatitis B, and/or history of hepatitis B infections, or known to be positive for HBsAg/HBV DNA.

208 History of chronic or active hepatitis C. Active hepatitis C is defined by a known positive hepatitis C antibody result and known quantitative hepatitis C virus RNA results greater than the lower limits of detection of the assay.

209 Unresolved toxicities from prior antitumor therapy, defined as not having resolved to Common Terminology Criteria for Adverse Events (CTCAE), version 5.0 grade 1 or to levels dictated in the eligibility criteria. Exception: myelosuppression (eg, neutropenia, anemia, thrombocytopenia), alopecia or toxicities from prior antitumor therapy that are considered irreversible (defined as having been present and stable for > 2 months) which may be allowed if they are not otherwise described in the exclusion criteria AND there is agreement to allow by both the investigator and Sponsor. Participants with ≤ grade 2 neuropathy may be eligible.

210 Current or recent (within 3 months of study drug administration) gastrointestinal disease such as chronic or intermittent diarrhea, or uncontrolled disorders that increase risk of diarrhea, such as inflammatory bowel disease.

Exception: non-chronic conditions (eg, infectious diarrhea) that are completely resolved for at least 2 weeks prior to starting study treatment.

- 211 History of (non-infectious) pneumonitis that required steroids or current pneumonitis.
- 212 Uncontrolled endocrine disorder including thyroid disease.
- 213 Subjects with active, known or suspected autoimmune disease. Exceptions: vitiligo, type I diabetes mellitus, residual hypothyroidism due to autoimmune condition only requiring hormone replacement, euthyroid subjects with history of Grave's disease (subjects with suspected autoimmune thyroid disorders must be negative for thyroglobulin and thyroid peroxidase antibodies and thyroid-stimulating immunoglobulin prior to first dose of study treatment), psoriasis not requiring systemic treatment, or conditions expected to recur in the absence of an external trigger.
- 214 History or evidence of any other clinically significant disorder, condition or disease that, in the opinion of the investigator or Sponsor, if consulted, would pose a risk to subject safety or interfere with the study evaluation, procedures or completion.

Prior/Concomitant Therapy

- 215 Autologous HSCT within 6 weeks prior to start of treatment.
- 216 Allogeneic HSCT within 5 years prior to start of treatment or active GVHD requiring systemic treatment.
- 217 Has had an allogenic tissue/solid organ transplant.
- 218 Prior treatment of AML with anti-CD33 chimeric antigen receptor (CAR) T cells.
- 219 Prior therapy with anti-PD-1 agent that was discontinued due to a grade ≥ 3 immune-related adverse event.
- 220 Antitumor therapy (chemotherapy, antibody therapy, molecular-targeted therapy, retinoid therapy, or investigational agent) within 14 days or 5 half-lives (whichever is shorter) of day 1. Exception: hydroxyurea to control peripheral blood leukemic cell counts is allowed until start of investigational product treatment.
- 221 Treatment with systemic immune modulators including, but not limited to, non-topical systemic corticosteroids, cyclosporine, and tacrolimus within 2 weeks before enrollment (day 1). Exceptions: physiologic replacement steroids or hydrocortisone for treatment of transfusion reactions.
- 222 Has received a live vaccine within 30 days prior to the first dose of study drug. Examples of live vaccines include, but are not limited to, the following: measles, mumps, rubella, varicella/zoster (chicken pox), yellow fever, rabies, *Bacillus Calmette–Guérin (BCG)*, and typhoid vaccine. Seasonal influenza vaccines for injection are generally killed virus vaccines and are allowed; however, intranasal influenza vaccines (eg, *FluMist®*) are live attenuated vaccines and are not allowed.
- 223 Major surgery within 28 days of study day 1 with the exception of biopsy and long line insertion. Note: If participant received major surgery, they must have recovered adequately from the toxicity and/or complications from the intervention prior to starting study treatment.

Prior/Concurrent Clinical Study Experience

224 Is currently participating in or has participated in a study of an investigational agent or has used an investigational device within 14 days prior to the first dose of study treatment.

Note: Participants who have entered the follow-up phase of an investigational study may participate as long as it has been 14 days after the last dose of the previous investigational agent.

Other Exclusions

225 White blood cells (WBC) $> 15 \times 10^9$ cells/L at screening.

226 Known hypersensitivity to immunoglobulins or to any other component of AMG 330 formulation.

227 Has severe hypersensitivity (\geq grade 3) to pembrolizumab and/or any of its excipients.

228 Women with a positive pregnancy test.

229 Women who are lactating/breastfeeding or who plan to breastfeed while on study through 120 days after receiving the last dose of study drug.

230 Men and women of reproductive potential who are unwilling to practice a highly effective method(s) of birth control while on study and for at least 120 days after receiving the last dose of study drug. Acceptable methods of highly effective birth control include sexual abstinence (men, women); vasectomy; bilateral tubal ligation/occlusion; or a condom with spermicide (men) in combination with hormonal birth control or IUD (women).

231 Subjects likely to not be available to complete all protocol required study visits or procedures, and/or to comply with all required study procedures to the best of the subject and investigator's knowledge. Has a history or current evidence of any condition, therapy, or laboratory abnormality that might confound the results of the study, interfere with the participant's participation for the full duration of the study, or is not in the best interest of the participant to participate, in the opinion of the treating investigator.

232 Has a known psychiatric or substance abuse disorder that would interfere with the participant's ability to cooperate with the requirements of the study.

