2.2 Background

2.2.1 Disease

AML is the most common form of acute leukemia in adults in the United States (US), with a rising incidence possibly due to an aging population, increased environmental exposure, and an increase in the population of cancer survivors previously exposed to chemotherapy and therapeutic radiation. In 2014, an estimated 18 860 new cases of AML were expected in the US with approximately 10 460 deaths from this disease ([American Cancer Society, 2014](#)).

Outcomes for most patients with AML remain poor ([Burnett et al, 2011](#)). In particular, relapsed disease is associated with unsatisfactory outcomes in the majority of patients ([Ravandi, 2013](#)). Although the majority of patients with AML initially achieve CR, over 60% will eventually relapse after a variable period of remission. Using the traditional cytotoxic chemotherapy regimens, the likelihood of achieving a second CR is low especially if the first CR was short in duration, particularly if less than 1 year ([Estey et al, 1996](#)).

Cluster of differentiation 33 (CD33) provides a useful target antigen for the treatment of patients with AML, as it is expressed on the cell surface of more than 90% of leukemia isolates from patients with AML with a very high average antigen density ([Krupka et al, 2014; Tanimoto et al, 1989; Scheinberg et al, 1989](#)). It is not expressed on tissues other than the hematopoietic system.

The PD-1 receptor-ligand interaction is a major pathway hijacked by tumors to suppress immune control. The normal function of PD-1, expressed on the cell surface of activated T-cells under healthy conditions, is to down-modulate unwanted or excessive immune responses, including autoimmune reactions. PD-1 (encoded by the gene *Pdcd1*) is an immunoglobulin (Ig) superfamily member related to cluster of differentiation 28 (CD28) and cytotoxic T-lymphocyte-associated protein 4 (CTLA-4) that has been shown to

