4.2.1 Replacement of Subjects

Ineligible subjects (ie, subjects who were exposed to AMG 330 or pembrolizumab, but post hoc were found to be ineligible) may be replaced. Subjects who do not meet the DLT evaluable criteria (see [Section 6.2.1](#)) may be replaced until at least 6 subjects become DLT evaluable in each cohort or at least 10 subjects in cohort 1 have been dosed through study day 28. If a sentinel subject in cohort 1 experiences a DLT at [REDACTED] μ g/day, [REDACTED] μ g/day or [REDACTED] μ g/day of AMG 330 during the first 14 days of monotherapy treatment in cycle 1, this subject will be defined as DLT evaluable and will not proceed

with the combination regimen. The sentinel role will be re-assigned to the next available subject.

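### The last exception in exclusion criterion 213 exempts autoimmune disease that is likely to return unprompted, which runs opposite to the exclusion it qualifies

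*Protocol*

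**What the plan says.** Criterion 213 in Protocol Section 5.2 opens by excluding "Subjects with active, known or suspected autoimmune disease". It then lists six exceptions. The first four are vitiligo, type I diabetes mellitus, residual autoimmune hypothyroidism managed by hormone replacement alone, and a history of Grave's disease in a subject who is now euthyroid. The list closes with "psoriasis not requiring systemic treatment, or conditions expected to recur in the absence of an external trigger".

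The last exception appears nowhere else. The synopsis only points back to Sections 5.1 and 5.2, and the SAP does not restate the criterion.

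Three other places bear on how the clause operates:

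- Protocol Section 5, introduction: "Prospective approval of protocol deviations to recruitment and enrollment criteria, also known as protocol waivers or exemptions will not be provided".
- Protocol Section 4.2.1: ineligible subjects, described as "subjects who were exposed to AMG 330 or pembrolizumab, but post hoc were found to be ineligible", may be replaced.
- SAP Section 9.3: eligibility deviations take their definition from the Protocol.

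**The concern.** An exception normally lets in the milder or better-controlled end of what a rule keeps out. This one does the opposite. It selects autoimmune conditions by their likelihood of returning spontaneously and exempts those, and it gives no exemption to conditions that need a provoking cause.

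The direction matters because pembrolizumab blocks PD-1. The Protocol's background (Section 2.2.1) says the normal role of PD-1 "is to down-modulate unwanted or excessive immune responses, including autoimmune reactions". Section 6.2.2.2.2 warns that adverse events seen with pembrolizumab may be immune related.

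What is at stake is who may be enrolled and who is later called ineligible. If one site follows the literal text and another follows the apparent intent, they would classify the same subject in opposite ways.

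**Working it through.** No arithmetic is involved. The check sets the wording of 213 against its own structure, the neighbouring criteria and the sections that use eligibility status.

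**1. The six exceptions compared**

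| Exception | Names a disease? | Limiting condition |
|---|---|---|
| Vitiligo | Yes | None |
| Type I diabetes mellitus | Yes | None |
| Residual hypothyroidism | Yes | Hormone replacement only |
| History of Grave's disease | Yes | Euthyroid |
| Psoriasis | Yes | No systemic treatment |
| Last clause | No | None; selects expected recurrence without a trigger |

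Five of six name a disease, and three of those five carry a limit. The last does neither. Because the exceptions are alternatives, it can also override the limits on the others: psoriasis that does need systemic treatment would be exempt under the last clause if it were likely to return unprompted.

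**2. The clause read both ways**, for a subject with one autoimmune condition outside the five named exceptions:

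| Condition likely to return without a trigger? | Literal text | With a negation inserted |
|---|---|---|
| Yes | Not excluded by 213 | Excluded |
| No | Excluded | Not excluded by 213 |

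The two readings disagree in both rows, so the choice between them settles the 213 status of every such subject.

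**3. A neighbouring criterion.** The exception in criterion 210 (gastrointestinal disease) covers non-chronic conditions that have completely resolved. It points the opposite way from the last clause of 213.

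**4. Whether other criteria cover the gap.** Seven other exclusions can catch some subjects whom the literal text of 213 lets through:

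- Four are specific: 210 (gastrointestinal disease), 211 (pneumonitis), 212 (uncontrolled endocrine disorder) and 221 (systemic immune modulators in the 2 weeks before enrollment).
- Three rest on judgement: 203 ("any clinically relevant concurrent disorder that may pose a risk to subject safety"), 214 ("in the opinion of the investigator or Sponsor, if consulted, would pose a risk to subject safety") and 231 (which includes that it "is not in the best interest of the participant to participate, in the opinion of the treating investigator").

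Criterion 214 concerns any other significant disorder, so a site could take autoimmune disease as already settled by 213. Being exclusions, these seven can correct only the first row of the table in step 2. They cannot restore a subject with a trigger-dependent condition whom 213 shuts out, and Section 5 allows no waiver.

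**5. Where eligibility status is used.** It permits replacement of an exposed subject (Section 4.2.1). It requires discussion with the sponsor about continuing treatment (Section 8, introduction). It is a listed reason for early removal from treatment (Section 7.1), and it feeds deviation reporting (SAP Section 9.3).

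It does not decide analysis membership. The Safety Analysis Set is all enrolled and dosed subjects (Protocol Section 9.3.1; SAP Section 6.1). DLT evaluability depends on a DLT, on exposure or on completing the evaluation period (Protocol Section 6.2.1).

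**The case against.** Every exception narrows its rule, so the clause is not a contradiction in formal logic. The Protocol already admits some known autoimmune disease by design, since vitiligo and type I diabetes are exempt without any limit. Section 2.2.1 describes PD-1 biology and sets no eligibility principle. The missing negation is an inference, and text may have been lost in reading the PDF.

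The list of seven covering criteria is also not exhaustive. Section 6.1.7 disallows chronic systemic corticosteroids and other immunosuppressive therapy from screening to end of study. Criteria 209 and 219 and the organ-function limits in Table 5-1 could also catch some of these subjects. With approximately 20 subjects and no prevalence figure, it is not shown that anyone would be affected, and a different eligibility label would not remove a treated subject from the main analyses.

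Most of this stands as a limit on the claim. The conflict is with the purpose of the exclusion, not with formal logic. The further criteria are again partial, and none readmits a subject. Divergent site readings are a possibility that the wording leaves open; the documents do not show that they occurred. The possible loss of text is why the sponsor is asked to check the source first. However, the sentence is grammatical and shows no redaction or gap. None of these points changes what the operative text says or supplies another reading of it.

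**Conclusion.** The concern holds. As written, the last exception in criterion 213 exempts an open-ended class of autoimmune conditions, chosen by expected spontaneous recurrence, and leaves trigger-dependent conditions excluded unless a named exception applies. This is an operative eligibility rule and should be fixed.

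Its size can be given only as scope. One of six exceptions is affected, seven other exclusion criteria give partial cover (four specific, three resting on judgement), and none of the seven can reverse an exclusion under 213. The number of subjects cannot be quantified. No effect on the DLT count, the cohort 2 decision, the sample size or the analysis sets is claimed.

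The conclusion assumes that the public text reproduces the source wording. That a negation was intended is likely but unconfirmed, and this review does not say which eligibility rule is right.

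**What to change.** The sponsor should check criterion 213 against the source protocol and confirm whether a negation is missing. If the source reads as the public text does, the last exception should be reconciled with the exclusion it belongs to, the criterion amended and the sites notified.

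The cost is one clause in a protocol amendment, with IRB/IEC submission (Protocol Section 11.3) and notice to approximately 5 sites (Section 4.2.2). Sample size and analyses do not change. If the source already carries the intended wording, the check alone is enough.
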